3. STUDY DESIGN

3.1. OVERVIEW

We will perform a randomized controlled trial of community-dwelling, older adult ED patients being discharged home to test the effect of a community-based, paramedic-coordinated, ED-to-home transitions program that has been validated in other settings.

In performing this program evaluation, we will adapt the hospital-to-home CTI program to the ED-to-home transition, and then we will test its outcomes. Specific research activities include:

- We will identify, hire, and train paramedics to serve as the CTI coaches.
- We will enroll 2400 older adults (age≥60) being discharged home from the ED at the University of Wisconsin Hospital & Clinics (1200 subjects) and the University of Rochester (UR) Medical Center-Strong Memorial Hospital or Highland Hospital (1200 subjects combined).
- We will enroll up to 2400 primary caregivers of the patient subjects being discharged home.
- We will randomize enrolled subjects to receive either the ED-to-home CTI (intervention group) or usual care (control group).
- We will perform research assessments at baseline (in the ED) and again via phone 4 and 30 days after discharge. We will also collect additional data from medical and administrative records to test our hypotheses, as well as from up to one informal caregiver per enrolled older adult (Figure 1).

Intervention group subjects (CTI program) will receive one home visit and up to 3 telephone calls to support their transition and provide coaching, as per the CTI guidelines. Control group subjects (usual care) will receive no additional services. All study procedures will be standardized at both sites.

[figure not shown]
Our analyses will provide empiric evidence on the value of this intervention, thereby guiding the dissemination and sustainability of such a program to improve older adults' health after ED care.

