3.3. RATIONALE FOR INTERVENTION

We will implement and test the CTI for the intervention group because of its demonstrated effectiveness and cost-effectiveness, its applicability to the ED patient discharged home, its efficiency, particularly relating to activities in the ED, and its widespread use. We have chosen to use community-based

paramedics as the coaches for the CTI because these individuals are highly trained, available in all communities, and are highly respected by patients. Thus, paramedics are able to perform these visits in follow up to ED visits rapidly. Given that the CTI program has been tested using lay people, trained paramedics should be able to perform the required duties.

Table 2: Measures

	Measures	Time	Source/Approach
1. Demo -	Patient age, gender, marital status, race, ethnicity, education level, primary language, home ownership, living status, home address	ED	Patient survey
	Patient relationship with PCP	ED	Patient survey
	Insurance plan / number	ED	Epic review
	Primary Care Medical Home certification level	ED	Health systems
2. Clinical	New home services (since ED visit)	Day 30	Patient survey
	ED medications prior to assessment, chief complaint, final diagnosis (ICD-10), discharge medications, and instructions	ED	Epic review
	CTI Coaching & Services Forms* Personal Health Record (PHR) Home Visit/PHR Discussion Checklist Follow-up Phone Calls Checklist Patient Activation Assessment Medication Discrepancy Tool Care Transitions Measure - 3	CTI Coach home visit & coach follow up calls	CTI program records
3. Covariates	Medical history, including Charlson Comorbidity Index	ED	Patient survey
	Healthcare: Medications, home services, ED / hospital use	ED	Patient survey/ Epic review
	Health Status: Short Form-12 ⁶⁸	ED	Patient survey
	Disability Status: ADL ⁶⁹	ED	Patient survey
	Cognition: Short Blessed Test (BOMC)	ED	Patient survey
	Social Isolation: PROMIS Social isolation short form	ED	Patient survey
	Depression: PHQ-9	ED	Patient survey
	Anxiety: GAD-2	ED	Patient survey
Health literacy	ED	Patient survey	
4. Outcomes			
	Family Caregiver Activation in Transitions	ED, Day 30	Caregiver survey
	Understanding of red flags	Day 4	Patient survey
	Medication changes implemented	Day 4	Patient survey
	Follow up with PCP, specialists, urgent care	Day 4, 30	Patient survey / Epic review
	Wallston's Perceived Health Competency Scale (PHCS)	ED, Day, 30	Patient survey, Caregiver survey

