Patient subjects randomized to the intervention arm (CTI program) must agree to one paramedic coach home visit and up to 3 follow up phone calls to deliver CTI program clinical care over 30 days. The paramedic coach home visit will ideally occur within 24 hours of ED discharge and take approximately 1 hour. This home visit will be scheduled at a time that is convenient for the subject. During the home visit the paramedic coach will review the subject's medications, educate on red flags and emphasize provider follow-up. The phone calls will reinforce the coaching information. These interactions are organized around the validated and nationally implemented CTI program.

In the event a participating subject is admitted to the hospital directly from the initial ED visit (i.e., the primary team changes its mind based on developing results), then the subject (and caregiver where applicable) will be removed from the study because they no longer meet study eligibility criteria.

Caregiver subjects will be asked to complete an ED survey and one follow up research survey by phone at approximately day 30. The ED survey will take approximately 15 minutes to complete, and the call will take approximately 10 minutes to complete and will assess outcome measures. All questions will be voluntary.

Randomization: Randomization will occur at the site-level and occur after the treatment team has indicated that the patient will be likely discharged home, and the subject or legally authorized representative (LAR) has consented to participate on the study and the baseline survey has been completed. At that point, the subject will be randomized. This will be a stratified randomization, based upon whether or not an informal caregiver provides significant support for the patient.

In the infrequent event that the patient is admitted after consenting for the study and being randomized (but before being discharged and leaving the ED), the patient subject (and caregiver where applicable) will be withdrawn from study as an investigator initiated withdrawal because the subject no longer meets eligibility criteria (i.e hospital admission).

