After the patient returns home, the paramedic coach will perform the home visit, within 24-48 hours ideally. During this visit, the coach will follow the program as they have been trained by [name] and his staff. They will coach the patient to reconcile medications; emphasize the importance of provider follow-up and practice obtaining an appointment and asking the PCP questions at the visit; review red flags due to medications and the acute condition; and develop the Personal Health Record. As per the CTI, the paramedic will not do the work for the patient, but will coach and educate the patient and/or caregiver. During the CTI program's follow-up calls (up to 3, not related to research activities), the paramedic coach will further coach and support the patient and/or caregiver.

If the subject expresses need for assistance beyond coaching or the coach identifies clinical issues, then he/she will coach the subject to call his/her provider to obtain further guidance. If the subject is unable to do so, then the paramedic coach will call the PCP directly or 911 to request an ambulance for evaluation and transport to an ED. Because the coach is a paramedic and has extensive medical training, he/she has the expertise to recognize medical issues and summon assistance.

All CTI program documentation will be securely retained within the study files in the UW Department of Emergency Medicine and the UR Department of Emergency Medicine. If the patient subject consents to the communication, a status summary will be sent to their primary care provider for inclusion in their medical record. This information will be sent using secure, HIPAA compliant email systems. Because all UW enrolled subjects will be patients of UWHealth, the UW email system will be used and is HIPAA compliant. Because all UR enrolled subjects will be patients of UR Medicine, the UR email system will be used and is HIPAA compliant.

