6.3. RESEARCH PROCESSES

The informed consent, baseline survey and randomization will be completed in the ED by the study RA. To facilitate scheduling the coach home visits the RA will know the coach's weekly availability. For those subjects randomized to the intervention group, the RA will schedule the coach home visit within 24 hours of ED discharge ideally and then send the paramedic coach the appointment time, patient's contact information and ED discharge summary via email. To ensure that all PHI is communicated securely, UW coaches will be provided with UW Department of Medicine email addresses and at UR the coaches will also be provided with UR email addresses. Thus, all communication will be within each institution's secure, HIPAA compliant email system.

Blinded research staff will be responsible for all research surveys for the patient and caregiver. These are intended for all subjects (control and intervention group) and independent of the clinical CTI program delivered to the intervention group.

Patient subjects will be contacted four days after ED discharge. The RA will telephone the subject and complete a survey that evaluates the program fidelity and initial outcome measures (Table 2). We chose this time point because patients should have made medication changes (e.g., started an antibiotic) and contacted their provider for follow up by then. We anticipate that the survey will take no longer than 10 minutes to complete.

Patient subjects will be re-contacted thirty days after ED discharge. The RA will re-contact all subjects and complete a final survey. We anticipate that the survey will take no longer than 10 minutes to complete the telephone survey. The RA will inform subjects of the research phone numbers from which all calls will be made. It is anticipated that providing this information will re-assure subjects and give an increase sense of comfort knowing who is calling them.

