12.2 PLANNED STATISTICAL ANALYSIS

Through the analytic methods used in Aims 2 and 3, we will assess differences between groups related to process outcome measures (Aim 2) and will assess the effectiveness and cost-effectiveness of the ED-to-home CTI (Aim 3). In Aim 4, we will identify predictors of repeat ED use among intervention group subjects. We will characterize of our study sample using descriptive statistics and corresponding measures of variation. We will assess for differences between groups at baseline despite randomization in key characteristics (e.g., demographics, comorbidities) using t-tests for continuous variables and Chi-square tests for categorical variables, using Fisher's exact test where appropriate. These comparisons will enable the identification of covariates to be controlled in our multivariable analyses. If distributional assumptions associated with a particular statistical procedure are violated, we will use appropriate transformations or non-parametric alternatives. Primary analyses will be performed under the intent-to-treat principle, keeping subjects in the group to which they were originally randomized, regardless of compliance or adherence to study procedures. We will conduct sensitivity analyses among subjects who complete all study procedures to evaluate the effect of the intervention among those who complete all study-related procedures. Hypothesis-driven comparisons will be made to control the family-wise type I error rate at 0.05 (two-sided) for the primary hypothesis.

Caregiver Subject Analysis: Although not an original aim of the study, we have obtained permission from the NIH and will perform a limited analysis of caregiver activation. This was only recently added to

the CTI. To compare the caregiver activation between the control and intervention groups, we will administer the FCAT. The FCAT will be scored as 1-6 points per question, for a score ranging from 10-60. We assume that 30% of participants will have caregivers with them, the average score will be 30, and we will look for a 5 point difference. Our sample size will allow a power of >0.8 for a t-test ($\alpha=0.05$).

Hyp 1A: More program participants will demonstrate understanding of their ED discharge instructions, red flags that indicate a worsening of their condition, and how to respond to the red flags three days after ED discharge.

Hyp 1B: More program participants will implement medication changes made in the ED within three days of ED discharge.

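### The completer sensitivity analysis conditions on an undefined post-randomisation state, so its result is not a randomised comparison if coaching counts, and needs an unstated assumption if it does not

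*Combined protocol and SAP*

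**What the plan says.** Section 12.2 keeps subjects in their randomised group for the primary analyses, "regardless of compliance or adherence to study procedures". It then says that the team will "conduct sensitivity analyses among subjects who complete all study procedures to evaluate the effect of the intervention among those who complete all study-related procedures". No section lists the procedures that count, their time windows, or a threshold.

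The procedures differ by arm. Both arms are asked for three surveys: in the ED, at day 4 and at day 30 (Section 5.1). CTI subjects must also agree to "one paramedic coach home visit and up to 3 follow up phone calls to deliver CTI program clinical care over 30 days". For the other arm, Section 3.1 says: "Control group subjects (usual care) will receive no additional services".

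The text supports two readings of completion:

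- **Surveys only.** Section 6.3 describes the surveys as "independent of the clinical CTI program delivered to the intervention group". Section 6.1 separates coaching from research in the same way: "follow-up calls (up to 3, not related to research activities), the paramedic coach will further coach and support the patient".
- **Coaching included.** The intention-to-treat sentence that comes just before the completer sentence speaks of compliance and adherence to study procedures. Read together, the completer set looks like the adherent set.

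The missing-data paragraph of Section 12.2 states an MCAR condition, with weighted GEE for MAR and a mixture model for non-ignorable non-response. It does not mention selection by completion.

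**The concern.** The stated aim is an intervention effect among completers. Randomisation makes the arms comparable as allocated. It does not make comparable two subsets picked by what happened later.

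If coaching counts, a CTI subject must receive a visit and calls inside the 30-day outcome window to qualify, while a control need only answer surveys. An early return to the ED could then remove a subject from one arm's set and not from the other's. With calls set at up to three, there is also no fixed number that makes the programme complete.

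If only surveys count, selection still follows randomisation. It distorts the odds ratio only if the link between returning and completing differs by arm.

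What is at stake is the meaning of a supportive result. A completer difference could be read as confirming or softening the primary finding when it partly reflects who stayed in the set.

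**Working it through.** The plan gives no figure for this analysis, so there is none to reproduce. What follows illustrates the mechanism.

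**Inputs from the documents.** Section 12.1: control risk 20%, design effect 20% against 15%, 1200 per arm, 25% attrition (1200 × 0.75 = 900). Home-visit timing: ideally within 24 hours in Section 5.1, but in Section 6.1 "the paramedic coach will perform the home visit, within 24-48 hours ideally". I use both ends.

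**Assumed inputs.** r is completion in returners divided by completion in non-returners, by arm. Returns are spread evenly over 30 days. Completion is 75% in non-returners.

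**Formulas.** Completer risk = p·r / (p·r + 1 − p). Completer odds ratio = true odds ratio × r(CTI) / r(control).

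**Surveys-only reading, r = 0.8 in both arms.**
- No effect: 0.16 / (0.16 + 0.80) = 16.7% in each arm, odds ratio 1.00.
- True 15% against 20%: 0.12 / (0.12 + 0.85) = 12.4% against 16.7%. The odds ratio stays at 0.71; the risk difference shrinks from 5.0 to 4.3 points.

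**Coaching-included reading, no true effect.** Suppose every return before the home visit cancels it, and r = 1 in controls.

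| Visit at | r(CTI) | CTI completers | Controls | Gap (points) | Odds ratio |
|---|---|---|---|---|---|
| Returners still visited | 1 | 20.0% | 20.0% | 0 | 1.00 |
| 24 hours | 1 − 1/30 = 0.967 | 19.5% | 20.0% | 0.5 | 0.97 |
| 48 hours | 1 − 2/30 = 0.933 | 18.9% | 20.0% | 1.1 | 0.93 |

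**False significance at two-sided 5%.** CTI completers number 1200 × 0.75 × (0.2r + 0.8) = 900, 894 and 888, against 900 controls. The standard error is about 1.9 points. The chance of a significant result favouring CTI is 2.5%, 4.7% and 8.3%. Counting both tails, it is 5.0%, 5.9% and 8.9%.

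This covers the home visit only. The coaching-included reading also requires calls later in the window, which are not modelled.

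**Precision of the alternative.** With controls receiving no programme, the complier-average effect is the intention-to-treat risk difference divided by the proportion visited. The intention-to-treat half-width is 1.96 × √(2 × 0.2 × 0.8 / n): 3.2 points at n = 1200 and 3.7 at n = 900. Dividing by an assumed proportion visited (treated as fixed):

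| Visited | n = 1200 | n = 900 |
|---|---|---|
| 90% | 3.6 | 4.1 |
| 75% | 4.3 | 4.9 |
| 60% | 5.3 | 6.2 |

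**The case against.** The case for leaving the plan alone has five parts.

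1. **Low stakes.** Intention-to-treat is primary, error control is claimed for the primary hypothesis only, and no section gives the completer result a decision role. This stands, and it limits how much weight the point can carry.
2. **Small figures.** Under the surveys-only reading with equal selection, the odds ratio does not move, and odds are the scale of Hypothesis 2B. Section 6.3 also lets staff survey subjects who are in the ED or on a ward, which should reduce loss linked to returning. Both stand. Against them, Section 3.2 says that subjects admitted to a skilled nursing facility are not surveyed, so some outcome-linked loss remains.
3. **Early returns may not cancel visits.** No section says that they do. This stands; in that case the gap is zero.
4. **The missing-data paragraph already states assumptions.** For survey outcomes (Hypotheses 1A, 1B and 2A) under the surveys-only reading, a completer analysis is a complete-case analysis and the MCAR condition is given. It does not cover the coaching-included reading. Nor does it cover repeat ED use, which can be observed in non-completers because record review can continue after contact stops (Sections 3.2 and 7).
5. **A complier analysis has its own untestable assumption.** This stands. Calls without a visit would breach it if receipt means the visit. Any effect of the scheduling and reminder card given in the ED (Section 5.2) would breach it if receipt means any coach contact.

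A reader might go the other way and infer a bias as large as the design effect. Completion of 53% in CTI returners, against 75% in everyone else, would give 15% against 20% from selection alone: 0.2 × 0.53 / (0.2 × 0.53 + 0.8 × 0.75) = 0.15. The documents give no such completion rates, so they do not support that inference.

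**Conclusion.** The point holds as a limited one. The completer set is undefined and formed after randomisation. If coaching counts, the stated completer effect is not a randomised comparison. If only surveys count, its odds ratio can be trusted only under equal selection across arms, which the plan does not state for repeat ED use.

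The size and direction of any bias are unknown. The 0 to 1.1 points describe one assumed mechanism, early returns cancelling the home visit, and are neither an estimate nor an upper limit for the set as a whole.

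Two stronger conclusions might be drawn, and neither is supported. The primary result is not compromised, because it does not condition on completion. Nor does the completer analysis necessarily favour CTI: that direction comes from the assumed mechanism. The change is worth making because it is cheap and uses data already planned.

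**What to change.** For repeat ED use, add a complier-average causal effect as a supportive adherence analysis:

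- **Instrument and receipt.** Use randomisation as the instrument. Define receipt as home visit done, from the CTI program records that Table 2 (Section 3.3) ties to "CTI Coach home visit & coach follow up calls". Repeat with receipt defined as any coach contact.
- **Population.** All randomised and discharged subjects whose outcome can be obtained from surveys, administrative data or medical records. Treat those who refuse further record review, or whose data are expunged, as missing under the methods in Section 12.2.
- **Estimate.** The intention-to-treat risk difference divided by the proportion receiving the programme, with a bootstrap or delta-method interval.
- **Statement.** Say that assignment is assumed to have no effect on return except through receipt. Present the result as the effect in those who received the programme, not as a robustness check on the primary result.

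If the completer analysis is kept, list what counts as completion in each arm, state the selection assumption, and label it descriptive rather than as the effect of the intervention in completers. That minimum alone would cure the missing definition.

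The cost is SAP wording and one short analysis, with no new data collection. The interval is wider, as shown in the working, and the analysis answers a different question from intention-to-treat.

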4. CHARACTERISTICS OF THE RESEARCH POPULATION

4.1. SUBJECT CHARACTERISTICS

Number of Subjects: We propose to enroll 2400 ED patient subjects into the study, with 1200 of the enrollments coming at UW and 1200 at UR Medical Center-Strong Memorial Hospital or UR Medical Center-Highland Hospital. Of the 2400 subjects, 1200 will be randomized to the intervention group and 1200 to the control group. We will also enroll up to one informal caregiver per ED patient, resulting in up to 2400 additional subjects. Thus, the total number of subjects potentially enrolled in this study is 4800.

Gender and Age of Subjects: All patient subjects will be age 60 years and older, as this is a concern of the older adult population. Both men and women will be enrolled.

Informal caregiver subjects must be age 18 or older, and will be either male or female, depending on who is identified by the patient subject.

Racial and Ethnic Origin: Individuals of all races and ethnicities will be included.

Vulnerable Subjects: Older adults are the focus of this study as these problems are not as prevalent for younger individuals; thus evaluating transitional care for them is of likely little benefit and any developed knowledge may not be translatable to older adults. We will implement safeguards to protect this population:

1. The study staff will not be directly providing ED clinical care to the participants, thus eliminating any potential coercion.
2. Decisional capacity will be evaluated by the RA obtaining consent to ensure that participants understand the risk and benefits of the study before obtaining informed consent, unless the Health Care Power of Attorney has already been activated. The decisional capacity evaluation process that will be used has been approved by the UR IRB. It assesses the potential subject's understanding of the study. This process is more conservative than the UW IRB policy "Research with Adult Participants Lacking Capacity to Consent" (Section II) as all subjects will be tested in this minimal risk study. The PI ([name], emergency medicine), co-I ([name], geriatrician), and project director ([name], psychology degree, extensive community health/social work experience working with vulnerable populations) will ensure that all RAs who conduct the capacity assessment will be fully trained.

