12 DATA ANALYSIS AND MONITORING

12.1 SAMPLE SIZE DETERMINATION

This study is designed to have adequate power to test the primary hypotheses that the CTI will result in lower odds of repeat ED use within 30 days of discharge compared to the control group (Hypothesis 2B). Based on published data, we expect 20% of the subjects in the control group to have at least 1 repeat ED visit within the 30-day follow-up period. In order to detect a 5% absolute decrease in the frequency of repeat ED visits with 80% power using a Chi-square test at a two-sided significance level of 5%, we will need 860 subjects per group. We anticipate approximately 25% attrition over the 30-day follow up period. As such, a final sample size of 1200 subjects in each group will be recruited for participation. We also calculated the minimum detectable effect size testing individual biomedical and psychosocial factors predicting repeat ED visit in Aim 4 for intervention group only. With an expected 15% baseline proportion of repeat ED visit, the sample size of 860 in the intervention group will have 80% power to detect an odds ratio (OR) of 1.3 per standard deviation of a normally distributed predictor. Similarly, 80% power is available to detect an OR ranging from 1.6-1.7 for a binary predictor prevalent in 30-50% of subjects.

We will also have to adjust for clustering by site in most of the analyses below.

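### The caregiver FCAT is scheduled in the ED and at Day 30, but the only analysis named for it is a t-test, with no baseline adjustment and no statement of which score is compared.

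*Combined protocol and SAP*

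**What the plan says.** The Caregiver Subject Analysis paragraph of section 12.2 describes a small comparison added outside the original aims. It says "To compare the caregiver activation between the control and intervention groups, we will administer the FCAT". On scoring: "The FCAT will be scored as 1-6 points per question, for a score ranging from 10-60". On assumptions, the last being the size of effect sought: "We assume that 30% of participants will have caregivers with them, the average score will be 30, and we will look for a 5 point". The method appears only in the sentence that follows: "Our sample size will allow a power of >0.8 for a t-test", at alpha 0.05. No SD is given.

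Table 2 (section 3.3) lists "Family Caregiver Activation in Transitions" among the outcomes, from the caregiver survey, in the ED and on Day 30. Section 5.1 has caregivers asked to complete an ED survey and one call at about Day 30, with every question voluntary. It places randomization after the baseline survey. Section 5.2 has patient and caregiver surveyed first and the allocation disclosed afterwards.

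Two general statements bear on the point. Section 12.1 says that most analyses will need adjustment for site. Section 12.2 says that tests of baseline differences will be used to choose covariates for the multivariable analyses. The models then set out in 12.2 concern patient outcomes; none is described for the FCAT.

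**The concern.** A score measured before allocation is usually the best single predictor of the same score a month later. When it is scheduled for collection and then left out of the comparison, the interval is wider than it need be, and a chance difference between arms at baseline carries through in part to the estimated effect.

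The general covariate rule in 12.2 does not repair this. It is tied to multivariable analyses, and none is set out for caregivers. Even if it were extended to them, baseline FCAT would enter only when the arms happened to differ on it, so the precision gain would usually be lost.

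The text also leaves open whether the t-test is applied to Day 30 scores or to changes. Those are different analyses with different precision, and the choice should be fixed before data are seen.

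**Working it through.** **Inputs from the documents.** Section 4.1: "Of the 2400 subjects, 1200 will be randomized to the intervention group and 1200 to the control group". Section 12.2: 30% of participants with a caregiver, mean score 30, range 10 to 60, target 5 points, alpha 0.05. Section 12.1: "We anticipate approximately 25% attrition over the 30-day follow up period".

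**Assumptions.** The 25% loss is stated in a calculation for patients and is applied here to caregivers. Two-sided testing is assumed, since sidedness is not stated for the FCAT. The documents give neither an SD nor a baseline to Day 30 correlation r, so ranges are shown. Equal SDs at the two times are assumed.

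**Sample.** 0.30 × 1200 = 360 caregivers per arm; 360 × 0.75 = 270 per arm after loss.

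**The plan's power figure.** An exact value cannot be reproduced without an SD, but the bound can be checked. The largest SD giving 80% power for 5 points is 5 / [(1.960 + 0.842) × √(2/n)]:
- n = 360: 23.9
- n = 270: 20.7

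The SD here is that of whichever score is analysed. The largest SD possible for a 10 to 60 score with mean 30 is √[(30 − 10)(60 − 30)] = √600 = 24.5. Power by normal approximation:

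| SD | n = 360 | n = 270 |
|---|---|---|
| 10 | >0.999 | >0.999 |
| 15 | 0.994 | 0.972 |
| 20 | 0.918 | 0.828 |
| 24.5 | 0.782 | 0.660 |

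The stated bound fails only close to the mathematical limit.

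**Gain over a t-test on Day 30 scores.** Adjustment multiplies the variance by (1 − r²) and the interval width by √(1 − r²). The equivalent sample factor is 1/(1 − r²). The half-width is 1.96 × SD × √(2/270) × √(1 − r²).

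| r | CI narrower by | Equivalent sample | Half-width, SD 12 | SD 15 | SD 20 |
|---|---|---|---|---|---|
| unadjusted | – | 1.00 | 2.02 | 2.53 | 3.37 |
| 0.3 | 4.6% | 1.10 | 1.93 | 2.41 | 3.22 |
| 0.5 | 13.4% | 1.33 | 1.75 | 2.19 | 2.92 |
| 0.7 | 28.6% | 1.96 | 1.45 | 1.81 | 2.41 |

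At SD 20 and n = 270, power for 5 points rises from 0.828 to 0.861, 0.918 or 0.983.

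**Gain over a t-test on changes.** The change has variance 2(1 − r)SD². Relative to the adjusted model this is 2(1 − r)/(1 − r²) = 2/(1 + r), which is 1.54, 1.33 or 1.18 at r = 0.3, 0.5 or 0.7. The adjusted model is the more precise under either reading of the plan.

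**Chance imbalance.** At SD 15 and n = 270, the standard error of a baseline difference is 15 × √(2/270) = 1.29. A difference of 1.96 standard errors is 2.53 points. It would shift an unadjusted Day 30 comparison by r × 2.53, which is 1.3 points at r = 0.5 or 1.8 points at r = 0.7, against a target of 5.

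**The case against.** The strongest reply is that nothing planned depends on this. The comparison is a small addition outside the aims, the unadjusted test is unbiased under randomization, and its interval already allows for chance imbalance. At SD 12 the half-width is 2.02 points before any adjustment, against a target of 5. All of that stands, and it limits the point to efficiency.

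It is also fair to say that the t-test is named only as the basis of the power statement. A t-test on changes would use the baseline score, so it is not established that the plan ignores baseline altogether. That stands too, but it leaves the analysis under-specified, and the adjusted model is more precise than either version.

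Four stronger readings might be inferred, and the documents do not support them:
- *Every caregiver will have a baseline FCAT.* Section 5.1 only asks caregivers to complete the survey, and its questions are voluntary. Any fix must therefore deal with missing baseline scores.
- *The t-test is biased, or the power claim is wrong.* Neither follows; the bound above 0.8 holds over nearly the whole possible range of SD.
- *This is the smallest comparison in the trial.* That cannot be verified. Hypothesis 1B concerns medication changes made in the ED, and the number of patients who have any is not given.
- *The caregiver-support randomization stratum must be in the model.* Only enrolled caregivers supply FCAT data, so most of them probably fall in one level and the term may add little.

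**Conclusion.** The point holds as one of efficiency and specification. A baseline FCAT is scheduled before allocation, the only test named makes no stated use of it, and the score to be compared is not defined. Using the baseline would narrow the interval by about 5% to 29% relative to a Day 30 t-test for r between 0.3 and 0.7, and would remove the effect of a chance baseline difference to the extent that the score is correlated over time. These percentages depend on the assumed r but not on the SD. The half-widths in points depend on both, and on the assumed 270 per arm. No conclusion on the primary outcome is affected.

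**What to change.** In the caregiver paragraph of 12.2, prespecify a linear model of Day 30 FCAT on arm, baseline FCAT and site. Site fits the general statement in 12.1. Report the adjusted mean difference with its 95% CI against the 5-point target, and keep the two-sample t-test on Day 30 scores as a check.

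Add a simple rule so that caregivers with a missing baseline score stay in the model, for example mean imputation with a missing indicator. Include the caregiver-support stratum only if it varies among enrolled caregivers. State the SD behind the power figure and whether the test is two-sided.

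The cost is a few sentences of analysis text. Both FCAT assessments are already scheduled, so there is no added data collection or burden on caregivers.
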